#### (3) simple, once-daily, pan-genotypic HCV treatment regimens

According to the prospective SHIM algorithm, certain conditions (e.g. decreased kidney function, cirrhosis) will trigger a referral to the hepatology center for specialist treatment. In other cases, the OAT physicians will be trained to prescribe the available DAA medications and provide adherence counseling. Given that the OAT patients show up at the clinics daily or on a regular basis, treatment will start as soon as the pre-treatment evaluation is complete. **Given the implementation science premise of this proposal, we will not control which regimens are prescribed by physicians.** On the individual level, the frequency of dispensing may vary depending on the patient's OAT clinic visit schedule, but should not be more frequent than once a week. HIV co-infection (present in almost half of the OAT patients) will be considered an indication for referral to an HIV clinic, but not the hepatology center. HCV treatment in HIV/HCV co-infected patients will be managed by the OAT physician in consultation with the HIV specialist.

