### 3.5.4 Primary Endpoints

Primary outcomes are based on the HCV treatment cascade:

- P1. Completing pretreatment evaluation (completing all clinical and laboratory assessment prescribed by the physician according to the SHIM algorithm);
- P2. Initiating DAA treatment (taking the first dose of DAA medication prescribed by the physician);
- P3. Achieving SVR12 (having an undetectable HCV RNA PCR result at 12 weeks after treatment completion).

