### 3.5.5 Secondary Endpoints

Secondary outcomes will include the interim cascade steps:

- S1a. Testing for HCV RNA;
- S1b. Assessment of fibrosis staging;
- S1c. Completion of DAA treatment (receiving the last prescribed medication supply);
- S1d. Testing for HCV RNA at 12 weeks after treatment completion;

Factors that affect treatment effectiveness:

- S2a. DAA treatment motivation (summary score measured by the investigator-developed questionnaire at baseline);
- S2b. DAA treatment adherence (defined as percentage of doses taken using two measures: visual analog scale administered at treatment completion, and pill counts at each dispensing visit);
- S2c. Treatment satisfaction (measured by investigator-developed questionnaire at treatment completion);

Treatment outcomes:

- S3a. Quality of Life (measured by SF-12 questionnaires at all four interviews);
- S3b. Re-infection (measured at 12 months after treatment completion among those achieving SVR).

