For the secondary outcomes S2b-c, we will collect data using a **paper-based adherence form** administered by clinical personnel during patient visits at treatment initiation, medication pick-up at 4 and 8 weeks, and treatment completion at 12 weeks after initiation. The baseline form will assess self-efficacy and anticipated barriers to treatment adherence for the whole treatment period. The follow-up forms will assess treatment satisfaction, past 30-day and 7-day adherence using visual analog scale [36], side effects, reasons for non-adherence, and reasons for treatment discontinuation (if occurred). At treatment completion, the form will additionally assess the readiness and anticipated barriers to SVR check at 12 weeks after.

For the secondary outcomes S2a and S3a and relevant co-variables, we will collect data using a **patient survey**. The survey will be conducted for the pilot patients and all 3 arms of the main phase at baseline, treatment completion (or 12 weeks after initiation if not completed or 16 weeks after the baseline if not started) and 12 weeks after treatment completion (or 24 weeks after treatment initiation if not completed, or 28 weeks after the baseline if not initiated treatment).

The baseline survey will be administered after confirmation of the diagnosis using HCV RNA test. Patients who will test negative for HCV RNA will be excluded from the following study procedures.

All patient surveys will be collected by an independent interviewer, using study ID via UIPHP REDCap server with clerical checking and patient safeguards described in detail in the human subjects section.

The surveys will include demographics, geospatial assessment, depression (PHQ-9), substance use, alcohol use disorders (AUDIT-C), HIV comorbidity and treatment history, Chronic Liver Disease Questionnaire-Hepatitis C Version (CLDQ-HCV) [37], trust in physician scale [38, 39], HIV risk behaviors, family and social support [40], drug use and mental illness stigma [41], and socio-demographic information.

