In addition, we have planned to test for a linear trend among the intervention levels for the proposed outcomes, testing that SHIM+ECHO > SHIM with No ECHO > SOC. We also plan to test the treatment effects using similar methods for OAT dropout strata separately. In addition to direct effects, mediation and moderation regression will be conducted as described by Donaldson. Testing will be conducted at a Bonferroni corrected type I error level of 0.025 to control for multiple testing. Secondary and process outcomes will similarly be tested. These measures and their subscales will be compared as pre/post and over time using one-way ANOVA/Duncan test, with general linear models to identify differences in treatment effect stratified by the geographic region (cluster). Mean scores will be normalized, with comparisons between the three groups, with the referent being SOC. To address multiple testing, we will use the Benjamini-Hochberg method of controlling the false discovery rate. We do not expect missing data to be a concern since most of the data on primary outcomes will be derived from clinical source documentation; for the survey data, we expect that we will collect more than 90% of the data at the 24-week time point. We will, however, explore all patterns of missing data and compare those with and without data to determine whether the data may be MAR or not MAR (i.e. eliminate the missing completely at random assumption). We will conduct sensitivity analyses using an appropriate missing data method, such as multiple imputation.

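### Follow-up survey dates depend on whether and when DAA treatment starts, so the between-arm quality-of-life comparison (S3a) has no common time point

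*Combined protocol and SAP*

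**What the plan says.** Section 3.5.6 applies one survey rule to all three arms. The first follow-up survey is due at "treatment completion (or 12 weeks after initiation if not completed or 16 weeks after the baseline if not started"), and the second at "12 weeks after treatment completion (or 24 weeks after treatment initiation if not completed, or 28 weeks after the baseline if not initiated treatment"). The same section puts "treatment completion at 12 weeks after initiation", so the schedule assumes a 12-week course. Time zero for non-starters is the baseline survey, not consent: "The baseline survey will be administered after confirmation of the diagnosis using HCV RNA test".

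Starting DAA is a primary outcome: "P2. Initiating DAA treatment (taking the first dose of DAA medication prescribed by the physician"). In the SHIM arms, Section 3.1.2 says "treatment will start as soon as the pre-treatment evaluation is complete". In the SOC arm, Section 3.1.1 relies on referral to hepatology centers. Neither section gives a lag in weeks.

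Quality of life is "S3a. Quality of Life (measured by SF-12 questionnaires at all four interviews"), although Section 3.5.6 and its schedule table provide three surveys. Section 3.5.8 analyses by intent-to-treat, extends the mixed-model approach to quality of life, and lists time trends among the covariates. For secondary measures it adds: "These measures and their subscales will be compared as pre/post and over time using one-way ANOVA/Duncan test". It also refers to a 24-week time point. Neither the time trends nor that time point has a stated origin, and no visit windows are given.

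**The concern.** Which clock a patient is on depends on whether DAA is started, and for starters the dates depend on when. Both happen after randomization, and both are what SHIM is meant to change. An intent-to-treat comparison of S3a at the first or second follow-up survey therefore pools starters, seen at the end of treatment or 12 weeks later, with non-starters, seen at fixed times. The mix and the dates can differ by arm. A difference in SF-12 scores would combine the effect of SHIM with differences in time since baseline.

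The rule can also hide part of what SHIM might achieve. An SOC patient who waits 12 weeks for DAA is first surveyed at week 24, when treatment ends. The survey does not capture the wait, so a quality-of-life gain from faster access could be missed.

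A patient not yet started at week 16 is due a survey as a non-starter. If that patient starts later, a survey falls due again at treatment completion. Nothing says which of the two enters the analysis.

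What is at stake is S3a and the other scales repeated in the follow-up surveys. P1-P3 come from charts and external verification, S2a is measured at baseline only, and S2b and S2c use the adherence form.

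**Working it through.** **Inputs from Section 3.5.6.** Non-starters are surveyed at 16 and 28 weeks after baseline. Starters are surveyed at start + 12 and start + 24, using the 12-week course. **Not in the documents:** the share starting and the lag to start in each arm. All such values below are assumptions.

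**Step 1: when the clocks agree.** t + 12 = 16 gives t = 4, and t + 24 = 28 gives t = 4.

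| Start week t | First follow-up | Second follow-up | Offset from non-starter |
|---|---|---|---|
| 0 | 12 | 24 | -4 |
| 4 | 16 | 28 | 0 |
| 8 | 20 | 32 | +4 |
| 12 | 24 | 36 | +8 |
| 16 | 28 | 40 | +12 |
| Never | 16 | 28 | 0 |

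A week-16 starter reaches treatment completion when a non-starter has the second follow-up survey.

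**Step 2: arm means if every eventual starter is counted at start + 12.** With share p starting at mean lag m, the mean time of the first follow-up is 16(1-p) + p(m+12) = 16 + p(m-4). The second is 12 weeks later. Assume exponential start times with median 4 weeks in SHIM (mean 4/ln 2 = 5.77) and 12 weeks in SOC (mean 12/ln 2 = 17.31).
- SHIM, 80% start: 16 + 0.8 × 1.77 = 17.4; second survey 29.4.
- SOC, 40% start: 16 + 0.4 × 13.31 = 21.3; second survey 33.3.
- SOC, 60% start: 16 + 0.6 × 13.31 = 24.0; second survey 36.0.

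The gap is 3.9 to 6.6 weeks.

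**Step 3: same inputs, but the week-16 survey counts for anyone not yet started.** Of SOC starters, 2^(-16/12) = 40% begin after week 16. The mean becomes 16 + p·E[(T-4)·1(T≤16)]. For an exponential with mean θ, E[T·1(T≤c)] = θ - (c+θ)e^(-c/θ). The expectation is 0.66 in SHIM and 1.68 in SOC.
- SHIM: 16 + 0.8 × 0.66 = 16.5.
- SOC: 16 + 0.4 × 1.68 = 16.7, or 16 + 0.6 × 1.68 = 17.0.

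The gap is 0.1 to 0.5 weeks. For the second survey there are two possibilities:
- Status fixed at week 16: add 12, giving 28.5 against 28.7 or 29.0.
- Status judged again at week 28: 28 + p·E[(T-4)·1(T≤28)], with expectations 1.54 and 5.11. This gives 29.2 against 30.0 or 31.1, a gap of 0.8 to 1.8 weeks.

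Individual times still vary: in SHIM the central 90% of first follow-ups runs from about week 12 to week 24.

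**Step 4: lags for which the late-starter rule makes no difference.** Let SHIM starters begin uniformly over weeks 0-4 (mean 2) and SOC starters over weeks 6-16 (mean 11). SHIM at 80%: 16 + 0.8 × (-2) = 14.4. SOC at 40%: 16 + 0.4 × 7 = 18.8. SOC at 60%: 16 + 0.6 × 7 = 20.2. The gap is 4.4 to 5.8 weeks.

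**Step 5: a wider grid with the Step 2 formula.** Take SOC at 10-50% starting with mean lag 4-16 weeks, and SHIM at 60-90% with mean lag 2-6 weeks. SOC minus SHIM runs from -1.8 weeks (16.0 against 17.8: SOC 10% at week 4, SHIM 90% at week 6) to +7.8 weeks (22.0 against 14.2: SOC 50% at week 16, SHIM 90% at week 2).

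**Step 6: fixed dates.** With everyone surveyed at 16 and 28 weeks, the planned gap is 0 for any share and any lag.

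**The case against.** The strongest reply is that the fallback dates look chosen to line non-starters up with patients who start at about 4 weeks, and that they limit the gap. That is largely right if the week-16 survey counts for those not yet started (Step 3). A reader might infer from Step 2 that the arms are surveyed 4 to 7 weeks apart. The documents do not support that figure: it depends on assumed lags and on ignoring the week-16 survey that late starters are due. They do not fix the direction either, since Step 5 includes gaps of both signs.

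A reader might also infer that the analysis treats the surveys as simultaneous. Section 3.5.8 does not say so, and its time-trends covariate could adjust in part if it meant weeks since baseline. The plan does not define it that way.

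Treatment anchoring has a purpose. S3a is listed among treatment outcomes, the last survey coincides with SVR confirmation, and the post-treatment surveys ask about barriers to monitoring. That is a good reason to keep such surveys for describing starters, but it does not give the randomized comparison a common time point. Finally, no bias in SF-12 scores has been shown. The documents say nothing about how scores move over a few weeks, so the size can be stated only in weeks.

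**Conclusion.** The concern holds as a design weakness in one listed secondary endpoint, S3a, and in the other follow-up survey scales. It follows from a written rule: assessment time depends on DAA initiation, and the clocks coincide only for a start 4 weeks after the baseline survey. The missing late-starter rule matters in its own right, because identical assumed inputs give a first-follow-up gap of 0.1 to 0.5 weeks or 3.9 to 6.6 weeks depending on which survey counts. Early SHIM starts with SOC starts at 6-16 weeks give 4.4 to 5.8 weeks whichever counts.

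All these sizes rest on assumed shares and lags. Time is measured from the baseline survey, which follows RNA confirmation; any arm difference in delay to RNA testing would add to a gap measured from enrolment. It would be wrong to conclude that the cascade results are compromised, because P1-P3 do not use the survey.

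**What to change.** Base the between-arm S3a comparison on 16 and 28 weeks after the baseline survey, the plan's own non-starter times, for every participant in all arms. There are two ways to do this.

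1. Give the two follow-up surveys at those times whatever the treatment status. This removes the planned gap with the same number of surveys, and is practical because OAT patients attend the clinic regularly. The cost falls on late starters. A week-12 starter would be surveyed 4 weeks into treatment and 4 weeks after completion, not at SVR12. Items on post-treatment monitoring would then have to be collected at the SVR12 contact. Treatment satisfaction is already on the adherence form and need not move.

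2. Keep the treatment-anchored surveys to describe starters at end of treatment and SVR12. Model S3a on actual weeks since baseline, estimate the arm contrasts at weeks 16 and 28, and state that the week-16 or week-28 survey is the one that counts for anyone not yet started. This needs only a text change, but survey timing stays tied to treatment and the contrasts lean on the model wherever starters have no survey near those weeks.

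Either way, define the origin of the time trends and of the 24-week time point, and reconcile the four interviews named for S3a with the three scheduled surveys.

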### 3.5.7 Retention in the study

Given our intent-to-treat approach to outcome evaluation, discharge from the OAT program, non-completion of clinical assessment, non-initiation or non-completion of treatment will not result in withdrawal from the study. Collection of clinical data at OAT clinics does not require patient's presence, and this will not be affected by retention.

To ensure sufficient retention in follow-up assessments, we will use several strategies used in our studies of PWIDs in Ukraine where retention in all cases exceeds 83% at 12 months, including: 1) providing compensation time for travel time and assessment costs; 2) detailed locator information, including contact information of a chosen contact person, usually a relative or a social worker; 3) maintaining regular contact through visits to OAT clinics.

### 3.5.8 Analytic plan

All analyses will be according to the principle of intent-to-treat, i.e., analysis of site and individuals within the site as randomized. The primary individual-level outcomes are achieving three elements of the HCV treatment cascade (diagnosed, treated, achieving SVR). We have powered the study based on a comparison of the proportions among the three groups (see below). The denominator for all cascade indicators is the number of OAT patients who are screened positive for HCV and are enrolled in the study. The numerators, the number who completed the pre-treatment evaluation, started DAA treatment and achieved SVR, will be obtained from the electronic clinical data collection system. Data will be assessed for missingness. A repeated measures likelihood based mixed model with missing at random (MAR) assumptions will be used for the analysis of the primary outcome to compare the three allocations, adjusted for the stratification variables (geographic region) plus age and gender. We will also adjust for covariates that are predictive of missingness to be consistent with the MAR assumption. Sensitivity analyses as described below will be done to assess this assumption, which is a reasonable starting point given missing data is expected to be low. Results will be displayed as point estimates with corresponding 95% confidence limits. The primary (and secondary) outcomes will be tested at the 5% (2-sided) significance level.

Hypotheses

1) OAT facilities implementing the simplified integrated model will have adoption and penetration of HCV care elements, that will ultimately result in improved patient-level outcomes like HCV cure compared to standard of care (SOC);

2) Compared to No ECHO, clinicians at ECHO-facilitated sites will have improved HCV care cascade outcomes.

Aim 3's analysis will involve three distinct strategies. First, we will examine the time difference in HCV cascade elements (% diagnosed, % treated, % achieving SVR), with sub-analyses for geographic area and OAT dropout +/- ECHO vs SOC setting. To do this, we will use a generalized mixed linear model (with a logit link), where group will vary by either study arm or by geographical area. Our dependent variables will include: 1) a binary indicator for whether an individual patient achieved the desired HCV diagnosis/treatment coverage cut-off (e.g. diagnosis coverage >80%), as previously used to measure comprehensive and holistic integrated primary care for PWID receiving buprenorphine [42]. The same approach will then be used for secondary individual outcomes (treatment motivation and adherence, treatment satisfaction, quality of life), which we have done previously when integrating addiction treatment into specialty services in the US [43] and Ukraine [12]. 2) treating the primary and secondary indicators as a continuous variables. Any changes in national guidelines that might influence HCV treatment availability would not be scored until after at least 1 year after publication in order to allow for uptake changes by clinicians. Our covariates will include time trends, client-level variables including demographic characteristics, fibrosis stage, treatment motivation and adherence, addiction severity and mental health measures, as well as organizational and provider level measures (from Aim 2).

In addition, we have planned to test for a linear trend among the intervention levels for the proposed outcomes, testing that SHIM+ECHO > SHIM with No ECHO > SOC. We also plan to test the treatment effects using similar methods for OAT dropout strata separately. In addition to direct effects, mediation and moderation regression will be conducted as described by Donaldson. Testing will be conducted at a Bonferroni corrected type I error level of 0.025 to control for multiple testing. Secondary and process outcomes will similarly be tested. These measures and their subscales will be compared as pre/post and over time using one-way ANOVA/Duncan test, with general linear models to identify differences in treatment effect stratified by the geographic region (cluster). Mean scores will be normalized, with comparisons between the three groups, with the referent being SOC. To address multiple testing, we will use the Benjamini-Hochberg method of controlling the false discovery rate. We do not expect missing data to be a concern since most of the data on primary outcomes will be derived from clinical source documentation; for the survey data, we expect that we will collect more than 90% of the data at the 24-week time point. We will, however, explore all patterns of missing data and compare those with and without data to determine whether the data may be MAR or not MAR (i.e. eliminate the missing completely at random assumption). We will conduct sensitivity analyses using an appropriate missing data method, such as multiple imputation.

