### 3.5.6 Data collection

Given the primary and secondary outcomes of interest, data collection for Aim 1 will include three main sources: clinical chart review data and quantitative survey of patients.

**De-identified medical chart review** data extracted by authorized clinic staff will inform outcomes P1-P3, S1a-d and S3b. We will use the electronic Simple Treatment Monitoring Application (STMA)

developed and used in our previous [35] and ongoing projects to collect detailed data on all relevant assessments and treatments, including HCV diagnostic tests, pre-treatment assessments, DAA treatment prescription, on-treatment and post-treatment monitoring, OAT admission and discharge, OAT medication prescription. The database will also collect information on important clinical covariates, including HIV, TB and HBV co-infection, mental health screening and its results, prescription of ART and other medications and side effects. STMA data will be collected on a monthly basis from all sites.

It is expected that physicians at the SHIM sites will comprehensively manage HCV care, and the medical charts and STMA will contain all up-to-date diagnostics and treatment information. However, all SOC sites' patients and possibly some SHIM patients will receive HCV services elsewhere, and their HCV-related clinical data will not be available at the OAT clinic. To ensure completeness of the key outcome data for all participants, we will use an external clinical data verification procedure, similar to one used in our ongoing IMPACT project. In order to avoid intervention contamination, this procedure is conducted by research staff, and not by OAT clinic personnel. At the end of each quarterly clinical data collection cycle, the data manager will generate the HCV treatment cascade report in STMA. For each patient who will not have information about any of the three primary clinical endpoints (HCV diagnosis, treatment initiation, post-treatment HCV RNA PCR) in the report, the interviewers will conduct a brief follow-up by phone. If the patient will report receiving this service, the interviewer will ask about when and where the service was received. At the second stage, the interviewers will contact the respective healthcare facilities to verify the receipt of the services and results (for assessments). This procedure will be enabled by a separate third-party disclosure agreement signed by the patient.

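### HIV co-infection, present in almost half of OAT patients and collected at every site, is not pre-specified as a covariate in any Aim 3 model; naming it would be a small gain in precision and pre-specification

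*Combined protocol and SAP*

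**What the plan says.** Section 3.1.2, step (3), states that "HIV co-infection (present in almost half of the OAT patients) will be considered an indication for referral to an HIV clinic". HCV treatment in these patients "will be managed by the OAT physician in consultation with the HIV specialist", so they stay in the integrated pathway with an added step.

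Section 3.5.6 says of the chart-extraction system: "The database will also collect information on important clinical covariates, including HIV, TB and HBV co-infection". It adds that "STMA data will be collected on a monthly basis from all sites". The patient survey also asks about "HIV comorbidity and treatment history".

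Section 3.5.8 describes two sets of models for Aim 3. The primary mixed model is "adjusted for the stratification variables (geographic region) plus age and gender", with one open clause: "We will also adjust for covariates that are predictive of missingness to be consistent with the MAR assumption". For the logit mixed model the text reads: "Our covariates will include time trends, client-level variables including demographic characteristics, fibrosis stage, treatment motivation and adherence, addiction severity and mental health measures", followed by organizational and provider measures. HIV is named in neither.

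Section 3.5.1 matches three clinics within each of four regions and randomizes one to each arm, giving 4 clinics per arm with a target of 40 patients each. No matching factor other than region is stated.

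**The concern.** The plan calls HIV an important covariate and collects it everywhere, but never assigns it to a model. It is common, it is known at baseline, and under SHIM it puts a further step on the way to treatment, so it could plausibly be related to pretreatment evaluation (P1) and DAA initiation (P2). Matching by region does not balance HIV between clinics inside a region, and four clinics per arm is few for chance to even things out.

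Two things are at stake. The first is precision: if HIV predicts the outcome, leaving it out keeps avoidable variance in the arm comparison. The second is pre-specification. Because the lists are open, HIV could be brought in after the data are seen, and an adjustment prompted by an observed imbalance is harder to defend than one written down beforehand.

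Some covariates that are named cannot do this job. Fibrosis assessment is itself a secondary outcome (S1b), and adherence exists only for patients who start DAAs. Both arise after randomization. HIV status fixed at enrolment does not have that problem.

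**Working it through.** The plan has no figure of its own on HIV imbalance, so there is none to reproduce.

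**Inputs from the documents.** Clinics per arm: 4. Patients per clinic: 40, so 160 per arm (3.5.1). HIV prevalence: almost half (3.1.2), taken as p = 0.47.

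**Inputs assumed.** The documents give none of these:
- within-region between-clinic SD of HIV prevalence, s: 0.10 to 0.15 (0.05 also run in the simulation);
- difference in outcome probability by HIV status, g: 0.10 to 0.20 (0.05 also run);
- residual between-clinic SD of the outcome, c: 0.05 or 0.10, with outcome proportions near 50%.

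**Step 1: imbalance between two arms.** It has a between-clinic part and a patient-sampling part:

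SD = sqrt(2 × (s²/4 + p(1−p)/160)), where p(1−p)/160 = 0.2491/160 = 0.001557.

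- s = 0.10: sqrt(2 × (0.0025 + 0.001557)) = 0.0901, or 9.0 points.
- s = 0.15: sqrt(2 × (0.005625 + 0.001557)) = 0.1198, or 12.0 points.

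Under a normal approximation, a given pair of arms differs by more than 10 points with probability 27% and 40% respectively.

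**Step 2: shift in the arm difference for a one-SD imbalance**, g × SD:

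| s | g = 0.10 | g = 0.20 |
|---|---|---|
| 0.10 | 0.9 points | 1.8 points |
| 0.15 | 1.2 points | 2.4 points |

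**Step 3: the yardstick.** Ignoring HIV, the standard error of the arm difference is about sqrt(2 × (c²/4 + 0.25/160)). This is 0.066 for c = 0.05 and 0.090 for c = 0.10. Simulation of 12 clinics of 40 in regional triplets, with no true arm effect and 20,000 runs per setting, gives 6.5 to 9.3 points over the whole grid.

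**Step 4: variance that adjustment can remove.** The ceiling is (g × SD)² divided by the total variance.
- Largest case (s = 0.15, g = 0.20, c = 0.05): 0.024²/0.0687² = 0.000576/0.00472 = 12%. The simulation gives 10.9%, a little less because the HIV coefficient must be estimated.
- Small case (s = 0.10, g = 0.10, c = 0.10): 0.0090²/0.0905² = 0.000081/0.00819 = 1.0%. The simulation gives 0.7%.
- With g = 0.05 the simulated gain is nil.

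**Step 5: bias and error rate.** In the same simulation the mean error without adjustment is about 0. The rejection rate is 4.6 to 5.3% with or without adjustment when clinics are the unit of analysis. Among trials where one arm has over 10 points more HIV (s from 0.05 to 0.15), the unadjusted estimate is off by about 1.0 to 1.8 points for g = 0.10 and 2.3 to 3.4 points for g = 0.20. Adjustment reduces this to at most 0.3 points.

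**The case against.** The strongest case against the point has four parts.

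**The lists are open.** A reader might infer that no Aim 3 model will adjust for HIV. The documents do not support that. The logit-model list introduces its client-level variables as examples, and the primary model admits covariates that predict missingness; either could bring HIV in. What stands is narrower: HIV is not pre-specified by name.

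**Imbalance is not bias.** A reader might also infer that the arm effect will be biased. Under randomization a chance imbalance is variance, and an analysis that models clinic variation covers it in the interval. This stands in full. One condition goes with it: a site random effect is written out for Aim 2 (3.4.4) but not clearly for Aim 3. That is a separate and larger matter, which an HIV term would not repair.

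**The size is small and assumed.** If the effect size of 0.20 in section 3.5.9 is read as Cohen's w with proportions near 50%, the targeted largest difference is 0.2/sqrt(8/9) = 21 points (one arm apart from the other two) to 0.2/sqrt(2/3) = 24 points (arms evenly spaced). A shift of 1 to 2 points would seldom change a conclusion. This stands, and it sets the weight of the point.

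**HIV is not obviously special.** TB, HBV, mental health screening and ART are recorded alongside it. The documents describe no HIV-specific route in standard care, and if HIV acts mainly through the SHIM referral step, that is effect modification, which a main-effect term does not capture. This stands in part. HIV is nevertheless the one covariate for which the documents state both a prevalence near one half and an added step in the pathway.

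**Conclusion.** The point holds as a minor matter of precision and pre-specification. A covariate that the plan itself treats as important, and collects in all arms, is assigned to no Aim 3 model by name. With four clinics per arm matched only by region, chance HIV imbalance with an SD of 9 to 12 points is plausible. One SD of it moves the arm difference by about 0.9 to 2.4 points, against a standard error of about 6.5 to 9.3 points, and adjusting removes roughly 0 to 11% of the variance.

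These figures rest on the assumed between-clinic HIV spread, HIV effect and residual clinic variation. If HIV has little relation to the cascade outcomes, the gain is close to nothing. The direction of any HIV effect is also unknown from the documents.

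**What to change.** In the primary model of section 3.5.8, add HIV status fixed at or before enrolment as a patient-level covariate alongside region, age and gender. Take it from the OAT chart and, where the chart is silent, from the baseline survey. Keep not documented as its own category, separate from negative. Fixing the date keeps out later HIV testing, which the arm may influence.

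Three safeguards belong with it:
- Section 3.5.6 gives the baseline survey only after a positive HCV RNA result, and RNA testing is itself a secondary outcome (S1a). Accept from the survey only HIV status that predates enrolment, and repeat the analysis with chart status alone.
- Tabulate HIV charting completeness by clinic, since the not-documented category could partly reflect record-keeping.
- In a logit model, adding a prognostic covariate changes the conditional odds ratio being estimated. Report the marginal risk difference as well.

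The cost is a few lines of analysis-plan text, with no new data and no change to care. A patient-level term uses no clinic-level degrees of freedom. The clinic random effect for Aim 3 should be stated in any case; the HIV term does not substitute for it.
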